### ***Synopsis***

Insomnia is the most common sleep disorder affecting millions of adults and is linked to daytime impairment. Insomnia is typically thought of as a symptom, secondary to a primary disorder, and often goes untreated for years. Medication (over the counter or prescription) and sleep hygiene are typical insomnia symptom treatments but they do not address the cause of the insomnia. Newer guidelines view insomnia as a co-morbid disorder needing independent treatment. Recent research has discovered high rates of sleep-disordered breathing (SDB) among insomnia patients; this co-morbid pairing is referred to as "complex insomnia." Several studies have revealed that treatment of SDB decreases insomnia.

This study will determine which of two different types of positive airway pressure (PAP therapy) modes are more effective in reducing sleep breathing events in chronic insomnia patients and in decreasing insomnia severity. Patients presenting to the clinic with a primary complaint of insomnia will be potential participants for this study. Following diagnostic polysomnography (PSG) testing, insomnia patients diagnosed with SDB and meeting inclusion criteria will be randomized to a PAP treatment arm, CPAP or ASV. No experimental devices will be used in this study, both CPAP and ASV are FDA approved for treatment of SDB and are in wide use in the USA. Participants will complete a series of three titration studies with their assigned PAP mode and attend a minimum of five clinical follow-up appointments over a 14-16 week timeframe. Titration PSG studies will assess PAP pressure needs to ensure that patients are receiving optimal therapy at all times during this study. Clinical follow-up visits occur every two weeks at which time objective data download information and subjective measures will be collected. PAP adaptation barriers will be addressed as they arise during the study, because it is important that participants are able to use PAP therapy nightly during participation in this protocol. Baseline scores on insomnia severity, sleep quality, subjective insomnia parameters, sleep related impairment, and quality of life will be compared to outcome measures at the 4 month mark. Pre-treatment and post-treatment objective improvements on sleep studies will also be compared including sleep breathing indices, sleep consolidation indices, and objective data download information.

This study will be funded by ResMed Corporation, San Diego, CA. Research will be conducted by the non-profit Sleep & Human Health Institute (SHHI) at Maimonides Sleep Arts & Sciences (MSAS) and SHHI in Albuquerque, NM. This project will take 1-2 years to complete.

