### **Secondary Endpoint Objectives:**

- Objective improvements on sleep studies
  - Sleep breathing indices (AHI, RDI)
  - Sleep consolidation indices (SE%, REM%, REM min)
  - Objective Data Download (% compliance; % use, AHI, flattening %)
- Subjective Validated Psychometric Instruments
  - Sleep related impairment (ESS, VAS-F, VAS-S, III, FSS, SDB-6)
  - Quality of Life/Impairment (FOSQ-10, QLESQ, HSCL)

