**Inclusion and Exclusion Criteria:**

## Inclusion criteria:

1.  $\geq 18$  years old
2. Primary complaint of insomnia when presenting at clinic
3. Diagnosis of moderate to severe insomnia through the Insomnia Severity Index (ISI) with a score  $\geq 15$
4. Meet diagnostic criteria of Insomnia Disorder (per American Academy of Sleep Medicine)
5. Diagnosis of SDB, either OSA as determined by an AHI  $\geq 5$  events/hour or UARS with a RDI  $\geq 15$  events/hour and AHI  $< 5$  events/hour
6. Naïve to treatment for sleep-disordered breathing (SDB), including CPAP, APAP, ASV; mandibular repositioning devices (MRDs), and any other nasal or oral therapy with a primary indication of treating SDB
7. Able to fully understand study information in English and sign informed consent

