##### **Third Encounter (in person, at sleep lab)**

1. PSG results discussion with research coordinator
2. Confirmation that the patient meets I/E criteria
3. Patient reviews and signs informed consent form
4. [name] conducts airway exam and answers patient questions.
5. Subject randomized to treatment arm
6. Completion of special baseline questionnaires
  - a. One week Sleep Diary (see below) with Global Morning Rating of Nightly Sleep
  - b. Insomnia Impairment Index

- c. Fatigue Severity Scale
- d. Intake Supplement

7. Schedule Titration #1

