## **Research Rationale for Procedures**

### **Titration #1 (Initial)**

Participants return to MSAS sleep lab for a full night titration study during which only their assigned mode will be used. They will be fit with several masks and, with the help of a sleep technologist, will identify the best mask to start the PSG with and use during the study. The sleep technologist will titrate PAP pressure settings for each participant following AASM guidelines to eliminate all abnormal SDB wave forms, consolidate sleep, and achieve REM sleep with the assigned mode. All titrations will begin with low pressures, as recommended by the AASM, to help improve adaptation. Pressure settings will be determined to eliminate all SDB events (including RERAs). We anticipate that within the CPAP group the following trend will occur: aggressive treatment of RERAs will require increased pressure settings; these pressures will lead to expiratory pressure intolerance (EPI) or intolerance; and, “down” titration will be necessary for patient comfort. The highest pressures tolerated by the patient may not be equivalent to the pressures needed to effectively treat all SDB events. We would prefer to use pressures that treat all SDB events (including RERAs), but this may be an unrealistic goal for the CPAP group during the titration or the early adaptation period. Although we don’t anticipate as much of an issue of EPI or intolerance within the ASV group, we will follow the AASM procedure of “down” titration if it is needed. To avoid EPI and to help patients adapt to PAP, it may be

necessary to start CPAP patients on settings that do not treat all SDB events and increase settings over time. This approach may also occur with some ASV patients, but we expect the proportion of ASV patients with intolerance to be smaller than those using CPAP.

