#### **Data Analysis:**

Primary analysis is a repeated measures ANOVA to test for a group by time interaction with calculated effect sizes (Cohen's d or Hedges g). The initial analysis will be with a single ISI score. Both study completers and intent-to-treat (ITT) analyses will be conducted, albeit this is an efficacy study therefore the ITT is not necessarily germane to the focus of the work.

Several other variables will be analyzed in similar fashion (breathing event indices, sleep consolidation indices, sleep diary metrics, addition secondary variable measurements). As indicated by post-hoc factor analyses, we may also conduct more advanced multi-variate analyses.

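### The Synopsis plans a pre/post comparison of device download data that has no pre-treatment value, and the planned group-by-time test would remove any difference between modes already present early in treatment

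*Combined protocol and SAP*

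**What the plan says.** The Synopsis announces: "Pre-treatment and post-treatment objective improvements on sleep studies will also be compared including sleep breathing indices, sleep consolidation indices, and objective data download information". It thus includes the device download in that comparison alongside the PSG breathing and consolidation indices. Secondary Endpoint Objectives lists "Objective Data Download (% compliance; % use, AHI, flattening" %) under a heading about objective improvement on sleep studies. It gives no baseline, time point or definition of change.

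Data Analysis makes a repeated measures ANOVA, testing the group-by-time interaction, the primary analysis. It then adds: "Several other variables will be analyzed in similar fashion". The variables it names are breathing event indices, sleep consolidation indices, diary metrics and further secondary measures. There is no separate rule for downloads.

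Inclusion criterion 6 requires patients to be "Naïve to treatment for sleep-disordered breathing (SDB), including CPAP, APAP, ASV" and other SDB therapies.

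**The concern.** A pre/post comparison needs a value from before treatment, and the download has none. The plan does not say what an analyst should do about this. If the planned interaction is applied to the downloads that do exist, every time point lies after randomisation and on treatment. The test then asks only whether the arms diverge further over time, not whether one mode gives lower device AHI or more use.

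This matters because the protocol expects the arms to differ early. Titration #1 (Initial) says it may be "necessary to start CPAP patients on settings that do not treat all SDB events and increase settings over time". It allows that some ASV patients may also start this way, but expects intolerance in a smaller share of them. It would accept lower starting pressures, preferably for one or two weeks at most, which is roughly the period covered by the first download. Which mode better controls breathing events is one of the trial's stated questions, and the download is its evidence from home use.

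**Working it through.** The plan gives no figure for this item to reproduce, and no SD, correlation or expected gap for any download measure. The first two steps therefore rest on the documents alone; the last two add an illustration.

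**1. Order of events**

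- Before entry: no prior PAP (Inclusion criteria, item 6).
- Third Encounter: consent, randomisation, then "Completion of special baseline questionnaires" (one-week diary, III, FSS, Intake Supplement). No device is involved.
- Titration #1, then issue of the device within 2 days (Equipment Set-up Procedure).
- First scheduled download visit: 10 to 14 days after set-up (Clinic Follow-up).
- Last download: weeks 14 to 16 (Final Datasets).

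The number of pre-treatment downloads is 0 by design.

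**2. Consequence by variable**

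- Device AHI and flattening %: there is no pre-treatment value, so pre/post change is undefined for every patient.
- % use and % compliance: the only possible pre-treatment value is 0 for everyone, so change = post − 0 = post. Nothing is lost, but the pre/post form adds nothing.
- PSG AHI, RDI and consolidation indices: a diagnostic PSG exists, so these are unaffected.

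**3. What the interaction measures when all downloads are on treatment**

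Let E be the between-arm gap at the first download and F the gap at the last. The change contrast is C = F − E. With more than two visits the same logic holds: a gap that is constant over visits goes into the group main effect and contributes nothing to the interaction.

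**4. Illustration**

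Assumptions: F = 0.80 SD (the size the plan uses for its net ISI effect, borrowed here for scale only); equal SD at both times; correlation ρ between first and last download; 25 per arm, all contributing; two-sample t test, two-sided 0.05. The SD of change is SD × √(2(1 − ρ)), so the standardised contrast is C / √(2(1 − ρ)).

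At ρ = 0.5, √(2 × 0.5) = 1. With half the gap present early, C = 0.80 − 0.40 = 0.40, and the power is 28.3%.

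| Share of final gap present early | C (SD) | Power, ρ = 0.3 | Power, ρ = 0.5 | Power, ρ = 0.7 |
|---|---|---|---|---|
| 0% | 0.80 | 64.9% | 79.1% | 94.7% |
| 25% | 0.60 | 42.0% | 54.7% | 76.5% |
| 50% | 0.40 | 21.6% | 28.3% | 43.2% |
| 75% | 0.20 | 9.0% | 10.7% | 14.6% |
| 100% | 0.00 | 5.0% | 5.0% | 5.0% |

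A direct comparison of the final level needs no baseline. Its power at 0.80 SD is 79.1% in every row, and 0.81 SD is detectable with 80% power. Change from the first download does better only when little of the gap is present early and ρ is high. C changes sign only if E exceeds F.

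**The case against.** The best defence is that this is loose wording in one Synopsis sentence. Secondary Endpoint Objectives does not define the download as a change, whereas the primary list uses the word change where it means it. Downloads are scheduled throughout treatment, and Final Datasets speaks of comparing CPAP with ASV. Titration #3 (Final) already makes PSG against baseline the main objective before/after comparison. A repeated measures ANOVA does not require a pre-treatment point and also yields a group main effect. Data Analysis reaches downloads only through its general reference to secondary variables, or by counting device AHI as a breathing index.

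Much of this stands, and it rules out several stronger readings that a reader might infer:

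- That the download endpoint cannot be derived at all. Only the pre/post form fails; on-treatment comparisons between arms are available.
- That the plan uses the first download, or the diagnostic PSG AHI, as the baseline. No section says so. The documents also do not describe how the device counts events, so they cannot show how far its AHI departs from scored PSG.
- That the result would reverse in favour of CPAP. This needs an early gap larger than the final one, and the documents give no figures for either.
- That downloads should leave the repeated-measures analysis altogether. The series is useful for describing the time course.

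The defence does not meet one point. The test the plan names is the interaction, it extends that test to secondary variables without exception, and for downloads the interaction is the wrong contrast.

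**Conclusion.** The concern holds in a limited form. That no pre-treatment download exists follows from the protocol's own sequence and needs no assumption. The pre/post comparison is therefore not computable for two of the four download variables and is redundant for the other two.

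The loss from using the interaction, or change from the first download, depends on how much of the mode difference is present early. The protocol suggests that some may be, but does not quantify it. In the illustration, power ranges from no loss to the 5% false-positive rate at ρ = 0.5, with 28% when half the gap is present early. These figures rest on an assumed 0.80 SD final gap, equal SDs and complete data. The effect is confined to one secondary item. It should be corrected before analysis, but it does not touch the trial's main conclusion.

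**What to change.** 1. Synopsis: take the download data out of the pre/post sentence. Keep before/after AHI and RDI for scored PSG, as Titration #3 (Final) already does.
2. Secondary Endpoint Objectives: list the download measures as on-treatment outcomes, separate from improvement on sleep studies.
3. Data Analysis: make the test for download measures the between-arm difference in on-treatment level over a stated common window, for example the last 14 nights before exit, with the whole period from set-up reported as well.
4. State the rule for nights without use. Count them as zero for % use and % compliance, including for patients who stop. Device AHI and flattening % have no value on such nights, so report them as conditional on nights used.
5. Keep the repeated downloads for a descriptive time trend by arm.

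The cost is wording in three sections, with no new data or visits. The small downside is that no improvement figure can be reported for download measures.

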## **ABBREVIATIONS LIST**

AASM – American Academy of Sleep Medicine  
ABPAP – Auto-Bilevel Positive Airway Pressure  
ADE – Adverse Device Effect  
AEC – Adverse Effects Checklist  
AHI – Apnea Hypopnea Index  
APAP - Automatic Positive Airway Pressure  
ASV – Adaptive Servo-Ventilation  
BMI – Body Mass Index  
BT – Bed Time  
CAI – Central Apnea Index  
CBT-I – Cognitive Behavioral Therapy for Insomnia  
CHF – Congestive Heart Failure  
COPD – Chronic Obstructive Pulmonary Disease  
CPAP – Continuous Positive Airway Pressure  
CRF – Case-Report Form  
DME – Durable Medical Equipment  
EIQ – Exit Interview Questionnaire  
EPI – Expiratory Pressure Intolerance  
ESS – Epworth Sleepiness Scale  
FDA – Food and Drug Administration  
FOSQ-10 – Functional Outcomes of Sleep Questionnaire  
FSS – Fatigue Severity Scale  
HSCL – Hopkins Symptom Checklist  
III – Insomnia Impairment Index  
ISI – Insomnia Severity Index  
ITT – Intent to Treat  
MRD – Mandibular Repositioning Device  
MSAS – Maimonides Sleep Arts & Sciences, Ltd.  
NAR – Nonallergic Rhinitis  
NDS – Nasal Dilator Strips  
OOB – Out of Bed  
OSA – Obstructive Sleep Apnea  
OTC – Over-The-Counter  
PAP – Positive Airway Pressure  
PAP-T – Positive Airway Pressure Therapy  
PGA – Patient Global Assessment of Sleep Questionnaire  
PHI – Private Health Information  
PLMD – Periodic Limb Movement Disorder  
PSG - Polysomnogram  
PUDS – PAP Units of Distress Survey

QLESQ – Quality of Life Enjoyment and Satisfaction Questionnaire

RCT – Randomized Controlled Trial

LDI – Respiratory Disturbance Index

RLS – Restless Leg Syndrome

SDB – Sleep-Disordered Breathing

SE – Sleep Efficiency

SHHI – Sleep & Human Health Institute

SOL – Sleep Onset Latency

SUDS – Subjective Units of Distress Scale

TIB – Time in Bed

TST – Total Sleep Time

UARS – Upper Airway Resistance Syndrome

VAS-F – Visual Analog Scale- Fatigue

VAS-S – Visual Analog Scale- Sleepiness

WASO – Wake After Sleep Onset

## ***Background***

Insomnia is the most common sleep disorder in the general population affecting millions, and difficulty staying asleep (sleep maintenance insomnia) is the most common presentation.(1-5) Chronic insomnia is linked to daytime impairment,(6) disability,(7) motor vehicle crashes,(8) workplace absenteeism(9) and errors,(8) and excess medical service utilization.(7) It also aggravates or increases risk for alcoholism,(10) depression,(11) diabetes,(12) obesity,(13) and stroke.(14) The economic burden of insomnia has been calculated in the tens of billions of dollars.(15;16)

Though insomnia is encountered routinely in primary care,(6;17;18) it often goes undiagnosed or untreated for years.(19;20) Disregard for insomnia complaints may be a function of physician training or knowledge;(21-23) conversely, patients may avoid discussing insomnia with their doctors or may not envision useful treatments for this sleep disorder.(24;25) The apparent lack of attention to insomnia care may occur as a result of a vast medical literature that defines insomnia as a symptom, secondary to a primary disorder (e.g. cancer or depression). When the primary condition is treated, insomnia presumably resolves.(26)

Treatment offered for insomnia usually consists of three approaches: basic sleep hygiene education,(27) over-the-counter (OTC) sleep aids, or sedative/hypnotics and other sedating medications by prescription.(5;6;18;28) For mild insomnia cases, sleep hygiene may prove cost effective and often yields satisfying results with minimal external coaching. Though no definitive epidemiologic studies on the application of sleep education or prescription of sleep aids by primary care physicians are available,(19) CDC and NHANES studies report sedative prescriptions are on the rise.(29;30) Notwithstanding, protracted use of prescription sedating medications (both indicated and off-label use) is a controversial subject.(31) Unquestionably, prescription sedatives help some insomnia patients in the primary care setting,(32;33) including some who use these medications nightly for several months(34) or potentially longer.(35;36) Clinical trials often report minimal complications(35;37) among a large proportion of sedative users, including long-term users, although it is not always as clear whether these patients are achieving optimal outcomes.(33) Counter to these observations, some reviews report sedatives are of limited(38) or no efficacy(39) for most chronic insomnia patients. Conventional wisdom suggests sedatives may be used frequently for short periods and then discontinued for myriad reasons. Last, emerging research has raised questions about increased risks for mortality,(40;41) suicidality(42) and other side-effects(43) associated with sedatives. Still, prescription sedatives for chronic insomnia represent only one form of treatment—a symptomatic therapy that may not lead to remission or cure when drug use ceases—thus, if this form of therapy fails to resolve episodes of sleeplessness, it is unclear how primary care physicians proceed with these patients.(21;44)

Newer perspectives and guidelines from the fields of sleep medicine(45) and psychiatry(42) view insomnia as a co-morbid disorder rather than a symptom, which then warrants independent clinical assessment and treatment. This point is key to the specialty of sleep medicine, whose main imperative seeks to determine whether or not the chronic insomnia patient is receiving an efficacious treatment,(5) which often leads to an assessment of whether pharmacotherapy is yielding optimal results. When pharmacotherapy is failing, it requires a more thorough sleep medical evaluation and usually a broader

array of therapeutic options.(5;21) In particular, pharmacotherapy failure raises suspicions for additional complex physiological etiologies for sleeplessness,(5) a direct indication for polysomnography (PSG) per American Academy of Sleep Medicine (AASM) guidelines.(5;46) Of potential clinical import, recent research focusing on PSG diagnostics revealed surprisingly high rates of the physiological disorder sleep-disordered breathing among insomnia patients(47-52)—referred to as “complex insomnia.”(53) Two studies revealed very high rates of obstructive sleep apnea (OSA) or upper airway resistance syndrome (UARS)(54;55) in hypnotic-dependent insomniacs seeking treatment at a sleep medical center specifically for the chief complaint of persistent insomnia symptoms despite sedating medication use.

The manifestation and recognition of complex insomnia should be relatively straightforward, especially in light of newer research. In a recent study(56) we found that of 1,035 patients with an insomnia disorder (insomnia severity index score >7 and daytime impairment attributed to insomnia) who sought insomnia treatment at a sleep medical center, 42% ranked a sleep breathing disorder as one of their main reasons for seeking treatment, 13% reported a concern about sleep breathing problems, and another 26% reported awareness of sleep breathing symptoms. Only 19% of the total sample lacked awareness or concerns about a possible sleep breathing disorder. Although we found a high prevalence of sleep breathing awareness, it was only through multiple layers of questioning that these symptoms were uncovered, which suggests polysomnography may be underutilized in insomnia patients with sleep breathing complaints due to inadequate screening and thus fewer referrals to sleep centers.

Despite these obvious findings about insomnia, we presume most doctor-patient relationships currently steer clear of the discussion of sleep breathing symptoms, perhaps because so many insomniacs are more desperate about not sleeping. In our own clinic, we often hear people remark, “Sure I snore, but that’s not why I came to your sleep center; I want to fix my insomnia.” Moreover, this combination of sleep disorders—Insomnia and SDB—creates clinical confusion, because each one causes sleep fragmentation effects, and both disorders present with overlapping symptoms such as non-restorative sleep, awakenings at night, and difficulty returning to sleep.(57;58) The complex insomnia co-morbidity may further complicate physicians’ efforts to assess pharmacotherapy efficacy due to their lack of familiarity with the intricacies and assessments of either or both sleep disorders. In theory, confusion arises when primary care physicians face the challenge of prescribing different drugs or revising dosages to treat residual insomnia symptoms(21) instead of considering potential co-morbid SDB and referral to a sleep center.(28) Identifying pharmacotherapy failure may also be obscured if drug efficacy estimates are based on limited knowledge(27) or influenced by vested interests.(59) Making matters worse, no formal standards are published to define pharmacotherapy failure for insomnia drugs.(5)

When pharmacotherapy failure is suspected in primary care settings, many factors may dissuade physicians from referring insomnia patients to sleep medical centers for sleep specialist consultations or to sleep medical laboratories for overnight testing. However, when primary care physicians suspect sleep apnea in an insomnia patient, they may use screening tools designed to capture typical sleep apnea patients(60) but not validated to assess SDB risk among insomnia patients.(61) As a result, false negative screens may further confound care.

In particular, primary care physicians as well as a fair number of sleep medicine specialists may never consider a sleep study evaluation, because it appears so expedient to simply address the number one complaint of the vast majority of insomnia patients: "Doctor, I wake up at night and can't go back to sleep." Prescribing a drug seems rational and logical, yet few physicians take the time to build a differential diagnosis to explain these nocturnal awakenings. Moreover, the vast majority of insomnia research implicates two primary and not mutually exclusive pathophysiological pathways: (1) innate hyperarousal; and (2) learned behavior. Both theories more or less assign the physiological aspects of insomnia to the somatized tension that may cause or be a result of learned behaviors or innate hyperarousal activity. Neither of these theories implicates sleep-disordered breathing as a major component to this process, despite the facts that sleep-disordered breathing creates hyperarousal activity all night long and has been reported to trigger awakenings in patients that lead to middle of the night insomnia.

Our center explored this problem by conducting a study on "What causes chronic insomnia patients to wake up at night?"(62) No one had ever looked at this issue in a prospective work, because most studies focus on the post-awakening problem of returning to sleep, which is usually attributed to hyperarousal.(7)

Hyperarousal theory posits insomnia patients suffer from a state of increased alertness or arousal during waking or sleeping periods.(63;64) As above, hyperarousal is innate or genetically predisposed (physiologically driven; e.g. increased somatic tension(65)) or learned through behavioral influences that promote excess alertness or arousal (psychologically driven; e.g. losing sleep over losing sleep(66)), both of which over-stimulate the mind with racing thoughts and ruminations that inhibit sleep. Hyperarousal creates vulnerability to nocturnal awakenings among individuals predisposed toward excess mental stimulation or conditioning influences, which then extends a brief awakening (e.g. 5 minutes) into a longer awakening (i.e. a period of insomnia). This theory explains the difficulty in returning to sleep (duration of an awakening), but no research explains how hyperarousal actually causes awakenings.(63;64)

Few researchers study or comment on subjective or objective causes of these awakenings. Ohayon's work is the most authoritative.(4) Among 8,937 adults surveyed from the general USA population, 35.5% reported frequent nocturnal awakenings. When queried on "motives for awakening," 75.5% reported needing to use the bathroom often or sometimes. Waking spontaneously, thirst or noise averaged 30 to 40%; children, bed-partner, or pain averaged 10 to 20%; and, hunger and breathing difficulties were about 5%.(4) While this research was detailed, no findings were objectively confirmed with polysomnography (PSG). However, it is intriguing that Ohayon found nocturia to be the most common factor in the sample in light of extensive research linking nocturia to sleep apnea via the pathophysiological mechanism of excessive release of atrial natriuretic peptide from the right atrium of the heart, which in turn overstimulates kidney production of urine through the night. (67)

In our prospective study,(62) we selected 20 chronic insomnia patients without previous sleep evaluations or testing who denied having symptoms of sleep disordered breathing. All patients completed an intake set of questionnaires as well as a qualitative interview to assess subjective reasons

for awakenings. The most common subjective reasons for nocturnal awakenings were unknown reason (50%), nightmares (45%), nocturia (35%), bedroom distractions (20%), and pain (15%). No patients identified sleep breathing problems as a cause. All patients underwent PSG to assess awakenings and their causes. Of 531 awakenings observed, 90% were preceded by a sleep breathing event (apnea, hypopnea, or respiratory effort-related arousal). Thus, in a sample of chronic insomnia patients with minimal or no risks for a sleep breathing disorder, based on conventional criteria 85% of the subjects suffered from co-morbid insomnia and sleep-disordered breathing. Although these findings in combination with the aforementioned findings of frequent sleep breathing complaints among insomnia patients presenting to a sleep center strongly suggest a critical role for sleep apnea among insomnia patients, there remains certain skepticism about the construct of complex insomnia as it relates to treatment.

In our work and that of Guilleminault and colleagues,(68-74) emerging research suggests complex insomnia represents a much more common condition than previously anticipated in contrast to the wealth of research that focuses on the psychophysiological basis of chronic insomnia. Some treatment research, while involving only small samples, points to the potential for sleep breathing to play a larger role in the etiology of chronic insomnia in a sizeable proportion of patients. Most of these studies have been anecdotal or cases series with a few randomized controlled studies.(68-74) Despite the weakness in many of these designs, particularly a lack of clarity in some protocols as to selection bias and diagnostic criteria for insomnia disorders, all the studies showed improvements in insomnia symptoms subsequent to treatment for sleep-disordered breathing regardless of the therapy mode (positive airway pressure therapy, oral appliance therapy, nasal/oral airway surgery, bariatric surgery, and nasal dilator strips).

Two of the more rigorous studies included our randomized controlled trial assessing the impact of nasal dilator strips (NDS) and SDB education on insomnia severity and SDB symptoms in chronic sleep maintenance insomniacs.(69) We found patients using NDS and receiving SDB education had significantly improved insomnia, sleep quality, and life satisfaction compared to a control group. The other study, a randomized crossover prospective study by Guilleminault et al. comparing CBT-I and surgical treatment for OSA in 30 complex insomnia patients,(74) showed surgical intervention was more successful in improving insomnia than CBT-I alone. Although patients receiving initial treatment with CBT-I also showed increased TST, once these patients completed the surgical arm of the study their TST was further increased and SOL was significantly decreased.

Missing from this body of work is a rigorously designed randomized controlled trial (RCT) of positive airway pressure therapy (PAP-T) for the treatment of chronic insomnia. Such a treatment approach must naturally be conducted if we are to learn how insomnia may or may not be influenced by sleep breathing events. In our own clinical and research experience, we have found that patients with insomnia and comorbid sleep-disordered breathing ("complex insomnia") often demonstrate greater difficulty in tolerating fixed CPAP devices due to the specific problem of expiratory pressure intolerance. Thus, we have progressed toward the use of advanced PAP technology such as auto-bilevel (ABPAP) or adaptive servo-ventilation (ASV) devices in the treatment of these patients, the latter device manifesting

the best results by eliminating expiratory pressure intolerance, central-like pauses or central apneas, any or all of which may arise in patients using fixed CPAP pressures.

Clinically, we have researched two different samples at our center for the value of using advanced devices to treat insomnia patients with sleep apnea. In the first study,(75) we looked at 56 patients who had failed standard PAP therapy and reported anxiety or psychiatric distress associated with use of PAP. While being titrated on standard PAP, all were diagnosed with complex sleep apnea and were subsequently switched to ASV, which resulted in significantly improved sleep efficiency, total REM sleep time, REM consolidation and decreased awakenings, arousals, and time awake during the night. Follow-up on 39 of the 56 patients showed significantly improved adherence indices of nights used and hours per night used compared to standard PAP. Germane to the current protocol, insomnia severity markedly decreased on the Insomnia Severity Index (ISI) (16.8 vs 9.7,  $p = .001$ ,  $d = 1.40$ ). In a more recent study,(76) we looked at follow-up data from 281 patients with moderate to severe insomnia (ISI>15) and diagnosed comorbid OSA or UARS who were using either ASV or ABPAP. We found that regular use (>20hrs per week) of ASV was associated with sizeable decreases in insomnia severity measured on the ISI (19.0 vs 11.9,  $p = .001$ ,  $d = 1.50$ ).

Finally, another and equally large barrier to any successful RCT with PAP-T for chronic insomnia patients involves the use of a PAP-T placebo device. By the nature of insomnia and by the expectation that a useful insomnia treatment should be demonstrated over a minimum of 3 to 6 months, in our opinion it is unreasonable that any insomnia patient, let alone any institutional review board would accept the notion of using sham PAP therapy for 3-4 months.

Thus, given the current standard of care in the field of sleep medicine, the most pragmatic initial PAP therapy RCT protocol would involve the use of fixed CPAP as the control in comparison to the experimental group with advanced PAP technology, which from our experience would be an ASV device.

We hypothesize the following:

- (1) The use of ASV PAP therapy would prove superior to standard fixed CPAP in decreasing insomnia severity on a validated insomnia research scale, increasing sleep efficiency by self-report and objectively on PSG, and improving additional subjective and objective markers of sleep quality.

